8.9.4 Increased Fibrosis in Response to Liver Injury

Subjects should be continuously monitored with laboratory analyses and physical assessment to ensure adequate liver function. FP-1305 should be withheld when Grade 2 (NCI-CTCAE version 5.0) AST, ALT or total bilirubin elevation is detected, and there is no evidence for cancer progression in the liver or other IMP non-related medical cause that might explain the increase. The IMP administration can be reinitiated when the liver enzyme values decrease to Grade <2 after discontinuation of FP-1305. If the adverse reaction recurs, indicating causal relationship to FP-1305, it must be permanently discontinued.

FP-1305 must be permanently discontinued if Grade 3-4 (NCI-CTCAE version 5.0) AST, ALT or total bilirubin elevation is detected in the absence of cancer progression in the liver or other IMP non-related medical cause that might explain the increase. For subjects with liver metastasis who begin treatment with Grade 2 AST or ALT, FP-1305 must be permanently discontinued when AST or ALT increases by ≥ 3 times from the baseline and lasts for at least 1 week in the absence of cancer progression or other IMP non-related medical cause that might explain the increase.

Proper diagnosis of the liver injury is encouraged.

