8.9 Management of Toxicities

All AEs should be graded according to [Section 11.3.1](#) and proper action taken based on the clinical findings and grading.

In the following, when a limit for a laboratory parameter in plasma is indicated and the local practice is to have the test in serum, the equivalent value should be considered, and vice versa.

FP-1305 should be withheld for any of the following adverse event at least possibly related to FP-1305:

- 1) Grade 2 pneumonitis (see [Section 8.9.2.1](#))
- 2) Grade 2 or 3 colitis (see [Section 8.9.2.2](#))
- 3) Grade 2 nephritis (see [Section 8.9.2.3](#))
- 4) Grade 2 liver enzyme elevations (see [Section 8.9.2.4](#))
- 5) Grade 2 or 3 endocrinopathy (see [Section 8.9.2.5](#))
- 6) Grade 2 fibrosis due to liver injury (see [Section 8.9.4](#))
- 7) Any other severe or Grade 3 treatment-related adverse reaction
- 8) Prolonged (> 2 weeks) Grade 2 or intolerable Grade 2 toxicity

FP-1305 must be permanently discontinued for any of the following adverse event at least possibly related to FP-1305:

- 1) Any life-threatening adverse reaction (excluding endocrinopathies controlled with hormone replacement therapy and/or immunosuppressants)
- 2) Grade 3 or 4 infusion reaction (see [Section 8.9.1](#))
- 3) Grade 3 or 4 pneumonitis or Grade 2 recurring pneumonitis (see treatment in [Section 8.9.2.1](#))
- 4) Grade 4 colitis (see [Section 8.9.2.2](#))
- 5) Grade 3 or 4 nephritis (see [Section 8.9.2.3](#))
- 6) Grade 3 or 4 hepatic failure (see [Section 8.9.2.4](#))
- 7) Grade 4 endocrinopathy (see [Section 8.9.2.5](#))
- 8) Grade 3 or 4 fibrosis due to liver injury (see [Section 8.9.4](#))
- 9) Inability to reduce the corticosteroid dose to 10 mg or less of prednisone or equivalent per day within 6 weeks from the initiation of the continuous corticosteroid
- 10) Persistent Grade 2 or 3 adverse reactions (excluding endocrinopathies controlled with hormone replacement therapy and/or immunosuppressants) that do not recover to Grade 0-1 within 6 weeks after the last dosing of FP-1305 and that are considered clinically significant
- 11) Any haematological or non-haematological Grade 3 treatment-related adverse reaction that recurs

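### For a first, unexplained Grade 3 AST, ALT or bilirubin rise, the Section 8.9 lists lead to withholding while Section 8.9.4 requires a permanent stop

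*Protocol*

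**What the plan says.** Section 8.9 of the protocol gives two lists, both for adverse events at least possibly related to FP-1305.

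- **Withhold list.** Item 4 is "Grade 2 liver enzyme elevations", with a reference to 8.9.2.4. Item 7 is a catch-all: "Any other severe or Grade 3 treatment-related adverse reaction".
- **Permanent-discontinuation list.** Item 6 is "Grade 3 or 4 hepatic failure", referring to 8.9.2.4. Item 8 is "Grade 3 or 4 fibrosis due to liver injury", referring to 8.9.4. Item 9 is "Inability to reduce the corticosteroid dose to 10 mg or less of prednisone or equivalent per day within 6 weeks" of starting continuous steroids. Item 10 covers clinically significant Grade 2 or 3 reactions that have not recovered within 6 weeks of the last dose, and item 11 covers Grade 3 reactions that recur.

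Section 8.9.4 sets its own laboratory rule: "FP-1305 must be permanently discontinued if Grade 3-4 (NCI-CTCAE version 5.0) AST, ALT or total bilirubin elevation is detected". The rule is conditional, because the sentence goes on to exempt rises that progression in the liver or a cause other than the drug might account for. Its paragraph on Grade 2 elevations allows a restart: "The IMP administration can be reinitiated when the liver enzyme values decrease to Grade <2 after discontinuation of FP-1305". The Grade 3-4 paragraph contains no such allowance.

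Section 8.9.2.4, on suspected immune-mediated hepatitis, withholds for Grade 2 enzyme elevation. It ties the permanent stop to Grade 3 or 4 hepatic failure, unless the increase is clearly due to progression in the liver.

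**The concern.** An investigator facing a first Grade 3 ALT rise is likely to start from the 8.9 lists, because they summarise when to pause and when to stop. If the lists and the detailed section disagree on a mandatory stop, handling can differ between sites.

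What is at stake is re-exposure after recovery. Section 8.9.4 rules it out. The lists never grant a restart after a Grade 3 reaction, but items 10 and 11 imply that one is possible: a stop for failure to recover within 6 weeks, or for recurrence, makes sense only if some subjects who recover are dosed again.

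Liver safety is a live subject in this trial. Section 11.5 reports hepatic involvement in four subjects and says that some of these events were graded life-threatening.

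**Working it through.** No arithmetic applies. The check takes one defined event through each text.

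**The event.** A first Grade 3 elevation of AST, ALT or total bilirubin, judged drug-related, without hepatic failure, without progression in the liver and without another non-IMP cause that might explain it.

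**Step 1: withhold list in 8.9.** Item 4 does not apply, because it stops at Grade 2. Item 6 concerns Grade 2 fibrosis. Item 7 applies if the event is not listed elsewhere.

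**Step 2: permanent-stop list in 8.9.**
- Item 1 (life-threatening reaction): not met by a Grade 3 laboratory rise as such.
- Item 6 (hepatic failure): not met, by the definition of the case.
- Item 8 (fibrosis): not met on its words, since an enzyme or bilirubin rise is not a finding of fibrosis.
- Item 9 (steroids cannot be tapered) and item 10 (no recovery in 6 weeks): may be met later, not at detection.
- Item 11 (recurrent Grade 3): not met by a first event.

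Result from the lists: withhold, through item 7.

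**Step 3: 8.9.2.4, where the list sends enzyme elevations and hepatic failure.** The permanent stop again names hepatic failure. The same sentence then speaks of an increase, which fits laboratory values better than organ failure. The sentence does not settle the matter.

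**Step 4: 8.9.4.** The grade and the exclusion condition are both met. Result: permanent stop at first detection, with no recurrence needed and no restart.

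**Step 5: neighbouring cases.**
- Grade 2: the lists and 8.9.4 both say withhold, so there is no conflict at first occurrence.
- Grade 4: the gap is smaller, because item 1 already stops life-threatening reactions.
- Grade 3 with another possible non-IMP cause: the 8.9.4 stop does not apply, so item 7 stands alone.

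The disagreement is therefore limited to Grade 3 and to the otherwise unexplained, first, related event.

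**Step 6: the two exclusion tests.** Section 8.9.2.4 lifts the stop only if progression in the liver clearly explains the increase. Section 8.9.4 lifts it if progression, or any other non-IMP medical cause, might explain it. Simply inserting laboratory elevations into 8.9.2.4 would leave one Grade 3 rise subject to two different tests.

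**The case against.** The strongest reply is that the texts can be obeyed together. The withhold list says *should*; 8.9.4 says *must*. Item 7 covers only reactions not dealt with elsewhere. Item 8 of the stop list points to 8.9.4, whose only Grade 3-4 criteria are AST, ALT and bilirubin, so fibrosis there may be shorthand for those values. The mention of an increase in 8.9.2.4 points the same way. The lists are not exhaustive either: 8.9.2.2, for example, adds a stop when other immunosuppressants are needed for colitis. Section 10.4 requires discontinuation for toxicities defined in 8.9, which includes 8.9.4.

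Most of this stands as evidence of intent: a permanent stop was probably meant, and a careful reader would let the specific rule govern. It does not make the wording agree. The lists treat enzyme elevations and fibrosis as separate items and send enzyme elevations to 8.9.2.4, where the reader again meets hepatic failure. The reference in 10.4 takes in the withhold list as well as 8.9.4, so it does not choose between them.

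A reader might go further and infer that the protocol authorises rechallenge after a Grade 3 liver rise. It does not: no text grants it, and the possibility is only implied. Nor does either route allow dosing to continue through the event. A reader might also take the DMC's role in 4.3.1, which covers subjects with a DLT once the MTD is reached, as overriding 8.9.4. That section is merely silent on liver events, and silence does not displace a mandatory stop.

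**Conclusion.** The inconsistency is real and narrow. For a first, drug-related, otherwise unexplained Grade 3 AST, ALT or total bilirubin elevation without hepatic failure, the literal wording of the 8.9 lists gives withhold and 8.9.4 gives permanent discontinuation. Both stop dosing immediately, so the practical difference is whether the subject could later be rechallenged. The conclusion rests on reading the list items by their words; if item 8 is taken as a pointer to the 8.9.4 laboratory criteria, the conflict disappears, and that is probably what was meant.

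No number of affected subjects or days can be attached to it. Section 8.7 lets treatment resume after two missed doses by documented agreement, so there is no firm outer limit to a restart, and 8.9.2.4 does not say whether dosing must wait for the end of a steroid taper. A reader might connect the point to the four hepatic cases in 11.5. The documents do not say whether any of them was an isolated first Grade 3 rise, or whether any subject was rechallenged, so no harm is shown. The case for correcting it is that it concerns a mandatory safety stop, the remedy is short, and sites should not have to infer the rule from a section headed as fibrosis.

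**What to change.** Three linked wording changes:

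1. Add an item to the permanent-discontinuation list in 8.9 for Grade 3 or 4 AST, ALT or total bilirubin elevation "in the absence of cancer progression in the liver or other IMP non-related medical cause that might explain the increase", with a reference to 8.9.4.
2. State in withhold item 7 that this event is excluded. A Grade 3 rise with another possible cause stays under item 7.
3. In 8.9.2.4, replace the permanent-stop wording based on hepatic failure with a cross-reference to the 8.9.4 criteria, so that one exclusion test applies. Item 6 can stay in the 8.9 list, so hepatic failure itself remains a reason to stop.

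The cost is a short text amendment, with no change to design, visits or analysis. The downside is the loss of a rechallenge option that 8.9.4 already forbids.

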8.10 Treatment beyond RECIST defined disease progression

In case of suspicion of pseudoprogression and subjective stable disease (no clinical deterioration), a second tumour evaluation should be carried out at least 4 weeks after the first response evaluation even if the subject has been deemed to discontinue from the study.

Subjects treated with FP-1305 may continue treatment beyond initial RECIST 1.1 defined progressive disease, assessed by the investigator, as long as they meet the following criteria (assessment of the criteria must be recorded in the source data):

- 1) Investigator-assessed clinical benefit
- 2) Tolerance of study treatment
- 3) Stable or improved ECOG performance status
- 4) Treatment beyond progression will not delay an imminent intervention to prevent serious complications of disease progression (e.g., central nervous system (CNS) metastases)

A follow-up scan should be performed after 4 weeks to determine whether there has been a decrease in the tumour size or continued progressive disease. The assessment of clinical benefit should be balanced by clinical judgment as to whether the participant is clinically deteriorating and unlikely to receive any benefit from continued treatment with FP-1305. If the investigator feels that the subject continues to receive clinical benefit by continuing treatment, the subject should remain on the trial and continue to receive monitoring. For the subjects who continue study therapy beyond progression, further progression is defined as an additional 10% increase in tumour burden with a minimum 5 mm absolute increase from the time of the initial progressive disease. This includes an increase in the sum of diameters of all target lesions and/or the diameters of new measurable lesions compared to the time of initial progressive disease. FP-1305 treatment should be discontinued permanently upon documentation of further progression.

8.11 Treatment Compliance

The Investigator and the trial personnel should ensure that each subject receives the right dose of FP-1305 as scheduled.

9 SUPPORTIVE TREATMENT

See [Section 10.1](#) and [Section 10.2](#) for allowed and prohibited interventions, respectively.

10 CONCOMITANT INTERVENTIONS / MEDICATIONS

10.1 Allowed Interventions

The subject's regular medication for other diseases

Palliative radiotherapy to bone metastases and non-target lesions on RECIST

Scheduled biopsies of the tumour

Corticosteroids with minimal absorption (topical, inhaled or intranasal) may be used if on a stable dose

All other interventions/medications/vaccines not listed in the prohibited interventions

10.2 Prohibited Interventions

Continuous use of immunosuppressive drugs

Systemic chemotherapy

Systemic corticosteroids other than replacement therapy (primary or secondary adrenal insufficiency) or used for treatment for infusion reaction, or as instructed in this protocol

Other investigational agents

Radiotherapy to the primary tumour or target lesions

Major surgery unless vital indication

Live (attenuated) vaccines

Medication that is necessary for the subject must not be stopped. Otherwise, prohibited interventions must be stopped prior to treatment with FP-1305 as defined in the exclusion criteria ([Section 5.1](#)); or at least five half-lives prior to treatment with FP-1305 if no definition is given in [Section 5.1](#).

If a subject requires treatment with systemic corticosteroids (oral or I.V.) after treatment with FP-1305 has been started this must be discussed and approved in advance (in written) by the Medical Monitor or the Sponsor (except for FP-1305 treatment related adverse effects as indicated in this protocol and emergency cases e.g. spinal cord compression and progressing brain metastases in which steroids are needed immediately as assessed by the Investigator).

10.3 Contraception and Pregnancy

Women of childbearing potential (i.e. not post-menopausal or surgically sterilised) must use highly effective methods of contraception (e.g. combined (estrogen and progestogen containing) hormonal contraception associated with inhibition of ovulation; progestogen-only hormonal contraception associated with inhibition of ovulation; intra-uterine device (IUD); intrauterine hormone-releasing system (IUS) or vasectomised partner) to prevent pregnancy or abstain* from heterosexual activity for the duration of the trial and for at least 3 months following treatment discontinuation. In addition, barrier contraception (with or without spermicide) may be used but this should not be considered as an adequate form of contraception on its own.

*Abstinence must be in line with the preferred and usual lifestyle of the subject. [Periodic abstinence (such as calendar, ovulation, symptothermal, post-ovulation methods) and withdrawal are not acceptable methods of contraception].

Fertile men whose partners could be of childbearing potential should routinely use a condom during the study and for 3 months thereafter. The partner, if not pregnant, should also use a reliable form of contraception such as the oral contraceptive pill or an IUD.

Refer to [Section 11.4.1](#) if a pregnancy is reported, either that of a female participant, or the partner of a male participant.

Female participants should not breast feed during the treatment period and for at least 3 months after the last infusion of the IMP.

10.4 Trial Subject Withdrawal/Discontinuation

Administration of the IMP and the subject's participation in the study must be discontinued for any of the following reasons:

- 1) Withdrawal of informed consent
- 2) In the case of any clinical AE, laboratory abnormality or illness leading to the conclusion by the investigator that participation into the trial is not the best interest of the subject
- 3) In the occurrence of toxicities as defined in [Section 8.9](#)
- 4) Pregnancy
- 5) Termination of the trial by the Sponsor
- 6) Loss of ability to freely provide informed consent
- 7) Inability to comply with protocol
- 8) Disease progression (for treatment beyond RECIST defined disease progression see [Section 8.10](#))
- 9) Dosing delays greater than the maximum allowed dosing delays as defined in [Section 8.7](#)

All trial subjects should comply with the protocol specified follow-up procedures as outlined in [Section 8.5](#). The only exception to this requirement is a withdrawal of informed consent for all trial procedures or when a subject has lost the ability to consent freely. All data collected until the withdrawal of informed consent will be analysed and included into trial data.

10.5 COVID-19 Vaccination

The outcome of the risk assessment conducted by Faron and the study team is that a COVID-19 vaccine given to a trial subject is considered as a simple concomitant medication with no interaction that requires advice on timing of the vaccine or any other aspect.

Treatment with FP-1305 during an ongoing round of vaccination will not, as far as Faron and the study team are aware of, compromise the efficacy of any COVID-19 vaccines. The study team will continue to review and monitor any update in terms of COVID-19 vaccine interaction with molecules targeting macrophages.

Investigators should follow the study protocol, local prescribing guidance and policies when considering if vaccination against COVID-19 is appropriate for subjects participating in this study.

11 ADVERSE EVENT REPORTING

11.1 Reporting Requirements

The collection and reporting of Adverse Events (AEs) will be in accordance with International Conference on Harmonisation (ICH) GCP, European Union, and national regulations and requirements. The definitions of different types of AE are listed in Appendix 4 - Definition of Adverse Events25.

In summary, the AE collection should comply with the following principles:

- 1) care should be exercised to collect AEs
- 2) follow-up period of 4 weeks (+/- 1 week; until follow-up visit) after the last dose does not have exceptions for AE collection. In circumstances where follow-up visit will not be performed, the follow-up period for AE reporting is 4 weeks from last dose of IMP.
- 3) if the study subject discontinues from the study, also collection of new AEs is discontinued at the follow-up visit, with the exception of follow-up for the IMP-related AEs (see [Section 11.6](#)). Survival information should be collected at 1 year and 2 years after the first IMP dose directly from the subject/caregiver or hospital records, or at 1 year after the last IMP dose if the treatment has been continued beyond one year
- 4) survival data collection after the last dose is not subjected for active AE collection
- 5) if an investigator becomes aware of a Serious Adverse Drug Reaction after the subject's discontinuation, or during the survival data collection period after treatment, this event should be reported immediately per the standard SAE reporting practices (see [Section 11.4](#))

11.2 Definition of Adverse Event

An AE is any untoward medical occurrence in a study subject or clinical trial subject administered a medicinal product and which does not necessarily have a causal relationship with this treatment.

An AE can therefore be any unfavourable and unintended sign (including abnormal laboratory findings), symptom or disease temporally associated with the use of an investigational medicinal product, whether or not related to the investigational medicinal product.

11.3 Adverse Events

It is the responsibility of the Investigator to collect all AEs (both serious and non-serious) derived by observation, by spontaneous unsolicited reports of subjects, and, where appropriate, by routine open questioning.

As this is a first in human trial, all medical occurrences which meet the definition of an AE ([Section 5](#)) should be recorded. Disease progression will be recorded as an AE/SAE in this study.

Any **pre-existing conditions** or abnormal laboratory findings present at screening should be recorded in the medical history and should not be recorded as an AE unless the condition worsens by at least one CTC grade during the trial.

Abnormal laboratory findings (e.g., biochemistry, haematology, urinalysis) or other abnormal assessments (e.g., vital signs) that are judged by the Investigator as clinically significant will, if certain requirements are met, be recorded as AEs or SAEs. Clinically significant abnormal laboratory findings or other abnormal assessments that meet the definition of an AE or SAE and are detected during the study or are present at screening and significantly worsen following the start of the study, will be recorded as AEs or SAEs. However, clinically significant abnormal laboratory findings or other abnormal assessments that are associated with the disease being studied (unless judged by the Investigator as more severe than expected for the subject's condition), or that are present or detected at the start of the study and do not worsen, will not be recorded as AEs or SAEs. The Investigator will exercise their medical and scientific judgment in deciding whether an abnormal laboratory finding, or other abnormal assessment is clinically significant.

The Investigator should assess the seriousness and causality (relatedness to the study medication) of all AEs experienced by the subject and this should be documented in the source data. The trial site is responsible for providing full details of AEs/SAEs in the electronic data capture system in the designated eCRF forms continuously during the trial.

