15.3.4.5 Safety

Safety and tolerability will be reported through the assessment of observed adverse events in the subjects. The number of cases and the number of subjects that these cases occurred in will be reported for each event. Drug-related events are reported in a separate table. In addition, both DLTs and drug-related serious adverse events are reported separately in a tabular format, and their seriousness will be assessed based on the NCI-CTCAE classification. AEs are also to be evaluated stratified by dose level and by disease group.

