The following variables will be evaluated for Part II of the study:

The demographic and baseline variables

Gender, age at entry, race, weight, height, medical history, concomitant medications/therapies (including prior cancer therapies), CMV infection status and pregnancy test (females of child-bearing potential), ECOG performance status, baseline tumour imaging results and HIV serology.

Part II

Primary outcome measure

- Safety and tolerability will be defined by physical examination, adverse events and by safety laboratory tests. Adverse events are collected, graded and reported according to the NCI-CTCAE version 5.0. MedDRA terminology will be used to classify, record, manage, and analyse the data. Tolerability of new dose(s) will be determined based on the occurrence/non-occurrence of dose limiting toxicity (DLT) during 28 days following the first dose of FP-1305 in subjects evaluable for DLT assessment in Part II.
- The response (ORR, CBR, and irORR separately) to the treatment will be determined by tumour imaging according to RECIST 1.1 based on images obtained by Cycle 7. Results from each tumour type, dose level and dosing frequency will be reported separately.

Secondary outcome measures

- The PK profile of a single dose (during Cycle 1) and repeated doses (during Cycles 2-5) of FP-1305 will be determined by repeated measurements of the drug concentration in the circulation. Peak concentration (C_{\max}), trough concentration (C_{\min}), area under the serum concentration versus time curve (AUC), clearance, volume of distribution, and terminal halflife ($t_{1/2}$) for each dose level will be determined. Results from each tumour type will be reported separately.
- Immunogenicity will be evaluated by assessing anti-drug antibodies in the circulation periodically during treatment and follow-up. Results from each tumour type will be reported separately.
- Potential predictive genetic, cellular and other markers will be associated with FP-1305 clinical activity as determined by ORR, CBR and irORR. This includes but is not limited to the correlation of response and immune cell profile, cytokine/chemokine profile and the proportion of CLEVER-1-positive monocytes, CD4, CD8, their ratio and regulatory T-cells in the circulation and in tumour specimens prior to treatment and in circulation during the first cycle of treatment.

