14.1 Adverse events

All recorded adverse events will be coded according to the Medical Dictionary for Regulatory Activities (MedDRA). Treatment emergent adverse event (TEAE) is defined as an AE that begins or worsens in severity after at least one dose of study drug has been administered. Non-treatment emergent AEs are listed only.

TEAEs will be summarized using frequency and subject count tables. TEAEs will be tabulated by disease group, system organ class (SOC), preferred term (PT), causality and severity. For analysis purposes, each subject will also be categorized by the maximum severity reported for a given TEAE (similar PT) and these will be tabulated by maximum severity. If feasible, the AEs will be summarised by treatment cycles.

Serious adverse events (SAEs) and AEs leading to discontinuation will be summarized by disease group.

Pooled AE data from Part I and Part II will be tabulated by dose. Immune-mediated TEAEs will be listed. AE of special interest (AESI) will be listed.

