20.1 Table and figure plan

List of planned tables:

Section 14.1
Disposition of subjects
Demographics and baseline characteristics
Medical history
Prior medications
Concomitant medications - other than chemotherapy or concomitant procedures
Concomitant medications related to chemotherapy or concomitant procedures
Extent of exposure and compliance
Section 14.2.1
Best response at any timepoint for Target-lesion, non-Target lesion and Overall response
Response by cycle
Simon's two-stage evaluation of stage one
Other response related information
Section 14.2.2
Monocytes CLEVER-1 positivity
S-CLEVER-1 and its occupancy by FP-1305
Serum concentration of FP-1305
Anti-human FP-1305 antibodies
Section 14.2.3
Lymphocyte subsets
B-cells

Regulatory T-cells
Circulating cytokines and chemokines
Change in LDH, LDL, CRP
Change in OxLDL
Change in CA-125
Change in CA19-9
Change in CEA
Change in CA-15-3
Change in AFP
Response with the immune cell profile by DCR and in total
The level of circulating cytokines and chemokines by DCR and in total
CLEVER-1 on circulating monocytes by DCR and in total
IHC parameters
Clever-1 and PD-L1 staining parameters
Overall survival
Overall survival (Cox regression)
Overall survival (Kaplan-Meier)
Progression free survival
Progression free survival (Cox regression)
Progression free survival (Kaplan-Meier)
Duration of response
Association of tumor responses to survival (Landmark analysis)
Length of latest prior treatment line for the cancer impact on survival
Length of latest prior treatment line compared to length of treatment in study
Subgroup evaluations
ECOG
Section 14.3.1
Overall summary of TEAEs
TEAEs by system organ class and preferred term
TEAEs by system organ class and preferred term by causality
TEAEs by system organ class and preferred term by severity
Serious TEAEs by system organ class and preferred term
TEAEs leading to discontinuation of study drug by system organ class and preferred term
Overall summary of pooled (Part 1 and Part 2) TEAEs by dose
Section 14.3.3
Hematology
Hematology shift
Chemistry
Chemistry shift
Urinalysis
Other lab parameters

Section 14.3.3

Vital signs
ECG
ECG maximum change
ECG abnormal findings
Physical examination

List of planned figures:

Section 14.2.4

Serum concentration of FP-1305
Lymphocyte subsets
B-cells
Regulatory T-cells
Macrophage HLA expression
Myeloid derived suppressor cell populations in circulation
Immune cell profile by DCR status and overall

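### Disease progression counts as an AE/SAE, and the Part II SAP does not separate it in the overall, serious, discontinuation and by-dose TEAE summaries

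*Protocol*

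**What the plan says.** Protocol 11.3, Adverse Events: "Disease progression will be recorded as an AE/SAE in this study". No exception is given. The same section explains the broad recording by the trial being first in human.

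Protocol 10.4 lists among the reasons for stopping the IMP "Disease progression (for treatment beyond RECIST defined disease progression see" Section 8.10).

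Part II SAP section 5 makes adverse events part of a primary outcome: "Safety and tolerability will be defined by physical examination, adverse events and by safety laboratory tests". DLTs are added for new doses.

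Part II SAP 14.1 defines a TEAE as an AE that starts or worsens after at least one dose. It then says "TEAEs will be tabulated by disease group, system organ class (SOC), preferred term (PT), causality and severity", and "Serious adverse events (SAEs) and AEs leading to discontinuation will be summarized by disease group". AE data pooled over Parts I and II are tabulated by dose.

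The Part II table plan (20.1) lists "TEAEs by system organ class and preferred term by causality", a serious TEAE table by SOC and PT, "TEAEs leading to discontinuation of study drug by system organ class and preferred term", and an overall pooled summary by dose. Neither 14.1 nor 20.1 says how progression terms are to be handled.

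Protocol 15.3.4.5 says "Drug-related events are reported in a separate table" and goes on to require separate tables of DLTs and of drug-related SAEs.

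**The concern.** Progression on treatment, or before the follow-up visit, starts after a dose and so meets the TEAE definition. Where it meets a seriousness criterion it is also a serious TEAE. Where the site records it as the event that ended dosing, it enters the discontinuation table as well. With no rule to flag it, the headline any-TEAE, any-SAE and discontinuation rates add up two different things: what the drug did to the subject, and the tumour not being controlled. The second is already measured by ORR, CBR and PFS.

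These rates are part of how a Part II primary outcome is described. A dose group or tumour type with less disease control would show more events in these tables even if toxicity were identical. The by-dose table has a further difficulty: in the originally enrolled Part II cohorts, dose and tumour type are not balanced.

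**Working it through.** **Plan's own figure.** There is none. The documents state no AE, SAE or discontinuation rate and no share due to progression. What follows is an illustration on assumed rates, anchored only to the design rates in protocol 15.7 (5% and 20%, applied there to clinical benefit).

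**Step 1. Which planned tables separate progression?**

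| Part II summary | SOC/PT rows | Causality split listed | Rule for progression terms |
|---|---|---|---|
| Overall TEAE summary | not listed | no | no |
| TEAEs by SOC/PT | yes | yes | no |
| Serious TEAEs | yes | no | no |
| Discontinuation TEAEs | yes | no | no |
| Pooled TEAEs by dose (overall summary) | not listed | no | no |

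No drug-related serious TEAE table is listed, although protocol 15.3.4.5 calls for one and Part II SAP section 16 reports no major deviation from the protocol analyses.

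**Step 2. How many progressors?** Let p = 1 − CBR, treating lack of benefit as progression (assumption). With CBR 20% to 5%, p = 0.80 to 0.95, which is 96 to 114 of the 120 subjects reported under this SAP.

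**Step 3. Share of all TEAEs.** Assume one progression event per progressor and m other TEAEs per subject. Share = p/(p + m).
- m = 1: 0.80/1.80 = 44% to 0.95/1.95 = 49%
- m = 2: 29% to 32%
- m = 5: 14% to 16%
- m = 8: 0.80/8.80 = 9% to 0.95/8.95 = 11%

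**Step 4. Share of SAEs.** Let q be the fraction of progressions reported as serious (assumed 10% to 100%) and t the fraction of subjects with another SAE (assumed 10% to 50%). Share = pq/(pq + t).
- Lowest: 0.08/(0.08 + 0.50) = 14%
- Highest: 0.95/(0.95 + 0.10) = 90-91%

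**Step 5. Share of AEs leading to discontinuation.** Let f be the fraction of progressions entered as the AE that ended dosing and d the fraction of subjects stopping for another AE (assumed 5% to 20%). Share = fp/(fp + d).
- f = 1: 0.80/(0.80 + 0.20) = 80% to 0.95/(0.95 + 0.05) = 95%
- f = 0.5: 0.40/0.60 = 67% to 0.475/0.525 = 90%
- f = 0.1: 0.08/0.28 = 29% to 0.095/0.145 = 66%

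**Step 6. Tumour mix by dose.** Part II SAP section 9 gives 1 mg/kg to every tumour type, and 0.3 and 3.0 mg/kg to colorectal cancer only, in the originally enrolled cohorts. Twelve cohorts of ten make 10 × 10 = 100 subjects at 1 mg/kg across ten tumour types, and 10 colorectal subjects at each of the other two doses. Suppose (assumption) that 95% of colorectal subjects and on average 80% of the 1 mg/kg group have progression entered as the event ending dosing, and that 5% stop for toxicity in each. The table would then read 100% against 85%: a 15-point gap with no difference in toxicity. The pooled table also adds Part I subjects, so this shows a direction and is not a forecast.

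**The case against.** The case against has real weight.

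- Serious and discontinuation TEAEs are tabulated by preferred term. Progression coded to its own term is a visible row, and a reader can allow for it.
- TEAEs are split by causality, and investigators can rate progression as not related. Protocol 15.3.4.5 requires drug-related tables.
- Part II SAP sections 10 and 15 report reasons for discontinuation. Protocol 10.4 lists clinical AE, toxicity and progression as separate reasons, so a progression stop need not be entered as an AE-caused stop. Section 8.10 lets some subjects continue past progression.
- The DLT definition (protocol 4.1) excludes events attributed to underlying disease. DLTs, not the AE tables, govern Part II escalation (4.3.1), and CBR governs expansion to Part III. Laboratory tests and physical examination are not driven by the progression rule.
- Routine AE collection ends at the follow-up visit, about four weeks after the last dose, so later disease deaths mostly stay out of these tables.
- Removing progression from the main tables of a first-in-human trial could hide drug-related worsening.

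These points limit the concern without removing it. Preferred-term rows do not correct the any-event counts, and none are listed for the overall or by-dose summaries. The causality split does not extend to the serious and discontinuation tables. Part II DLTs cover only the first three to six subjects of new-exposure cohorts over 28 days. The last point stands in full, and is why the all-events tables should stay.

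A reader might infer that the primary safety summaries mostly count the efficacy outcome, or that tolerability cannot be read from them. The documents support neither. They give no rates. In the illustration progression is a minority of all TEAEs throughout, anything from minor to dominant among SAEs, and predominant among discontinuation AEs only if a large part of progressions is entered that way. Nor does any passage make the pooled by-dose table the basis for choosing a dose.

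**Conclusion.** The point holds as a gap in presentation. If the plan is followed as written, the headline overall, serious, discontinuation and by-dose TEAE rates mix progression with toxicity, and the existing separation is only partial. The discontinuation table is the most exposed.

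The size cannot be stated. The illustrative ranges rest on treating absence of clinical benefit at the 5-20% design rates as progression, and on assumed rates of other TEAEs, SAEs and AE-related stops. They also depend on how sites enter progression, which the documents do not settle. The by-dose tumour imbalance is documented for the originally enrolled Part II cohorts; its effect on the table is not quantified. The missing drug-related serious TEAE table is a direct mismatch between protocol 15.3.4.5 and SAP 20.1 and needs no assumption. Overall this is a cheap improvement that makes the tolerability figures readable, not a flaw that invalidates the safety analysis.

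**What to change.** Leave AE collection and expedited reporting as they are. In Part II SAP 14.1 and 20.1:

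1. Pre-specify the list of preferred terms that count as disease progression.
2. Keep the all-events tables, and also show the overall, severity, serious, discontinuation and pooled by-dose summaries without those terms.
3. Add a drug-related serious TEAE table, as protocol 15.3.4.5 requires.

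The cost is a paragraph of SAP text, one programming flag and a few extra tables. Nothing changes at the sites, and because the all-events versions remain, no event is lost from view.
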